This patient population cannot utilize conventional amplification due to the severity of the hearing loss and poor speech discrimination abilities in the affected ear. Current treatment options include: contralateral routing of the signal (CROS) hearing aids, and bone-conduction devices. A CROS hearing aid is a two-part system that includes a microphone/transmitter on the affected ear and a receiver on the normal hearing ear. The microphone/transmitter sends the acoustic signal from the affected ear to the receiver, which is presented to the normal hearing ear. Bone-conduction devices utilize a percutaneous, implanted titanium abutment to send the acoustic signal from the affected side to the normal hearing ear via vibrations. The goal of both of these technologies is to send the signal from the affected side to the normal hearing side, thereby leaving the patient in a unilateral listening condition.

Though CROS hearing aids and bone-conduction devices provide the patient with auditory information from both sides to the better hearing ear, the ability to use binaural cues for speech perception in noise is variable (Kunst et al, 2007), and localization abilities have been found to be at chance (Bosman et al, 2003; Hol et al, 2010). For instance, Bosman et al (2003) compared three listening conditions in SSD subjects: unaided, CROS hearing aid and bone-conduction hearing aid. Subjects were allowed 4 weeks of listening experience for habituation with the CROS and bone-conduction hearing aids. Subjects reportedly experienced no difference in localization abilities between each condition, indicating the current technology available to this population could not improve localization abilities over the unaided condition.

It is of interest whether cochlear implantation of the affected ear would benefit the SSD population. A cochlear implant is a two-part system, including the internal electrode array and external speech processor. The internal electrode array is surgically implanted into the affected cochlea. The external speech processor receives sounds and transmits this signal to the internal portion. The electrode array presents the acoustic signal via electrical pulses within the cochlea, which is interpreted by the brain as sound. A steady growth in speech perception acquisition has been reported in conventional cochlear implant subjects up to 6-12 months of listening experience with the external speech processor (Pelizzone, Cosendai, & Tinembart, 1999). Presumably, cochlear implantation may provide the SSD population improvements in speech perception in the affected ear, which cannot benefit from appropriately fit hearing aids. Cochlear implantation may provide a benefit over current treatment options in the SSD population, as it stimulates the auditory pathway on the affected

side, thus allowing for ipsilateral representation of acoustic signals arriving to each ear independently.

Bilateral stimulation of the auditory system has been shown to improve speech perception in spatially-separated noise and localization abilities. These gains have been reported in bilateral cochlear implant recipients (van Hoesel & Tyler, 2003; Nopp, Schleich & D'Haese, 2004; Grantham et al, 2007). For instance, Grantham et al (2007) assessed the localization abilities of bilateral cochlear implant subjects at approximately 5 months of listening experience and then again 10 months later. The authors reported localization abilities did not differ significantly between these two intervals, indicating the ability to use binaural cues for improved localization developed after even limited listening experience with the external speech processors. Considering this subject population has bilateral hearing impairment, it is of interest whether the performance acquisition would be different in an SSD case with cochlear implantation since there is the added benefit of a normal hearing ear.

Cochlear implantation has been reported as a viable treatment option in cases of unilateral hearing loss, including sudden sensorineural hearing loss (Firszt et al, 2012), and severe tinnitus (Vermiere & Van de Heyning, 2009; Van de Heyning et al, 2008). Further, cochlear implantation has been shown to offer superior speech perception in noise, localization abilities, and subjective report in SSD cases as compared to CROS hearing aids and bone-conduction devices (Arndt et al, 2011). The limitation to this comparison, however, was the subjects had limited listening experience with the alternative treatment options (i.e. CROS hearing aids or bone-conduction device). Though other studies reported no difference in abilities with these technologies after 4 weeks of listening experience (Bosman et al, 2003), long-term duration of listening experience may influence speech perception and localization abilities. Considering this, a control condition of long-term users of current treatment options (i.e. bone-conduction devices) may provide a more accurate comparison with SSD cochlear implant recipients.

The primary goal of this project is to determine whether subjects with SSD experience an improvement in speech perception, localization, and quality of life with a cochlear implant as compared to an unaided listening condition. Secondary aims include: 1) a comparison of speech perception, localization, and quality of life outcomes in the study population to a SSD control group with long-term listening experience with a current treatment option (i.e. bone-conduction device), and 2) a within-subject comparison of speech perception and localization abilities with cochlear implantation versus the bone-conduction test device.

III. Objectives

- A. The primary purpose of this feasibility study is to demonstrate the effectiveness of cochlear implantation in subjects with SSD
 - 1. Postoperative results will be evaluated with speech perception measures, localization tasks, and subjective reports

- B. Compare outcomes of cochlear implantation to that of current treatment options (i.e. bone-conduction devices) for SSD cases
 - 1. Compare speech perception, localization, and subjective outcomes to a control group of implantable bone-conduction device recipients
 - 2. Assess cochlear implant subjects with a bone-conduction test device and/or previous BAHA device at the preoperative and 12 month follow-up intervals
 - a. Comparison of individual subject speech perception and localization abilities between the cochlear implant and bone-conduction device

IV. Definitions

Adjusted Constant Error: the rms deviation of the mean responses from the diagonal, computed after compensating for bias. This procedure reduces the bias when evaluating the relationship between the average response on the azimuth and signal source on the azimuth.

Bimodal: Cochlear implant in one ear and a conventional hearing aid in the contralateral ear

Bone-Conduction Device: A device on the poorer hearing ear that picks up the acoustic signal on the effected side and transmits to the better hearing ear via vibrations through the skull. This is accomplished by either securing the oscillator to the head with a headband or via a percutaneous, implanted titanium abutment.

Cochlear Implant (CI): A two-part system, including the internal electrode array and external speech processor that stimulates the auditory pathway on the effected side. The internal electrode array is surgically implanted into the affected cochlea. The external speech processor receives sounds and transmits this signal to the internal portion. The electrode array presents the acoustic signal via electrical pulses within the cochlear space, which is interpreted by the brain as sound.

Constant Error: the rms deviation of the average responses from the source positions

Contralateral Routing of Signal (CROS) Hearing Aids: A two-part system consisting of a transmitter microphone on the deafened ear and a receiver on the normal hearing ear. The transmitter sends the signal from the deafened ear to the normal hearing ear. The auditory pathway on the normal hearing ear receives the sound.

Interaural Level Difference (ILD): The difference in sound level between the two ears, dependent on the location of the sound source and the orientation of the head. This binaural cue is typically dominated by high frequencies.

Interaural Timing Difference (ITD): The difference in the time a sound arrives to one ear as compared to the other, dependent on the location of the sound source and the orientation of the head. This binaural cue is typically dominated by low frequencies.

Pure Tone Average (PTA): The average threshold (dB HL) from 500, 1000, and 2000 Hz

Random Error: the standard deviation of responses at each signal source position, averaged across all potential signal sources

Root-Mean-Square (rms) Error: The difference between the location on the azimuth of the sound source and the subject's response on each trial for the localization task

Single-Sided Deafness (SSD): Severe-to-profound sensorineural hearing loss with limited speech perception in one ear and a normal to mild hearing in the contralateral ear

V. Investigational Device

A. Subjects will be implanted with the commercially available MED-EL CONCERT cochlear implant with the standard electrode array (MED-EL Corporation, Innsbruck, Austria). The device consists of a stimulator, a coil with a magnet within its center, a reference electrode, an EAP reference electrode and an active electrode permanently attached to the stimulator. The electrode is made of medical grade silicone, platinum (electrode contacts) and platinum/iridium (90/10) wires and nitinol.

The purpose of the device is perception of environmental sound and potential for improvement in communication abilities.

For the adult population, the MED-EL CONCERT cochlear implant is indicated for those 18 years of age or older, who have bilateral sensorineural hearing impairment and obtain limited benefit from appropriately fitted binaural hearing aids.

The standard electrode array is 31.5 mm long, with 12 pairs of contacts spaced over 26.4 mm with 2.4 mm spacing between each contact pair. The electrode's length allows insertion into the scala tympani and stimulation of the cochlear canal to the fullest extent possible. The array features a marker ring 31.5 mm from the apex that is used to seal the cochleostomy and to indicate maximum electrode insertion. The diameter of the array increases to 1.3 mm at the proximal thicker part of array just before the marker ring.

Subjects will be fit with the Opus 2 speech processor. The Opus 2 speech processor is an external component of the MAESTRO Cochlear Implant System and is indicated for use on patients who have been implanted with a MED-EL cochlear implant. The Opus 2

audio processor consists of the control unit with the earhook attached, the battery pack frame and cover, the connecting piece, the coil and the coil cable. The audio processor uses batteries that provide sufficient power for both the external and the implanted electronics.

The MAESTRO 6.0 Fitting Software will be used to program the Opus 2 speech processor. The MAESTRO 6.0 software, which is used for different intraoperative and postoperative purposes for the MED-EL Cochlear Implant System. Currently, it contains the implant Telemetry and Fitting of the OPUS 1 or OPUS 2 processor, ART (Auditory nerve Response Telemetry) and ESRT (Electrically Evoked Stapedius Reflex Threshold), and Audiogram functions. The MAESTRO software is an external component of the MED-EL Cochlear Implant System and is intended to be used in a clinical or office environment by persons adequately skilled and trained to perform all intended tasks and with patients who received one of the intended MED-EL cochlear implants.

VI. Study Duration

- A. Enrollment Period
 - 1. 4 years

B. Study Timeline

- 1. Cochlear implant subjects
 - a. Each subject's involvement will last approximately 1.5 years, including: candidacy evaluation, preoperative evaluation, surgical procedure, initial activation of the external speech processor, and post-initial activation evaluations (1, 3, 6, 9 and 12-months post-initial activation)
- 2. Bone-conduction device control group
 - a. One evaluation interval to complete the test battery outlined in section VII.D.

C. Study Endpoint

- 1. Cochlear implant subjects
 - a. The 12-months post-initial activation interval
- 2. Bone-conduction device control group
 - a. Completion of the test battery (1 interval) defined in section VII.D.

VII. Methods

All procedures will be conducted by UNC investigators, including board-certified otologists, audiologists, and speech-language pathologists. Fully informed consent will be obtained from all subjects.

A. Participants: CI subjects

Subjects must meet the following inclusion criteria and not exhibit any of the exclusion criteria.

- 1. Inclusion Criteria
 - a. Unilateral moderate-to-profound sensorineural hearing loss
 - i. Unaided residual hearing thresholds measured from 250-8000 Hz (PTA ≥70 dB HL in the ear to be implanted)
 - ii. Normal to mild residual hearing thresholds from 250-8000 Hz in the contralateral ear (≤35 dB HL at each frequency, 250-8000 Hz)
 - b. Greater than or equal to 18 years of age at implantation
 - c. Duration of moderate-to-profound sensorineural hearing loss less than or equal to 5 years
 - i. Either reported by subject or documented in previous audiograms
 - ii. Can be less than or equal to 10 years if the subject consistently utilized hearing technology (such as a bone conduction device or conventional hearing aid) within the past 5 years
 - d. Previous experience with a current treatment option for SSD, including a conventional hearing aid, bone-conduction device, or CROS/BICROS technology.
 - i. At least one month of listening experience with device
 - ii. Dissatisfaction with and/or discontinued use of current treatment option due to: insufficient gain, poor sound quality, and/or lack of perceived benefit.
 - e. Aided word recognition in the ear to be implanted of 60% or less as measured with CNC words (50-word list)
 - i. When listening with an appropriately fit hearing aid and masking applied to the contralateral ear
 - ii. Aided testing will be conducted in a sound-proof booth with the subject seated 1 meter from the sound source, facing 0° azimuth. Recorded materials will be presented at 60 dB SPL.
 - iii. The hearing aid output will be measured using NAL-NL1 targets.
 - f. Realistic expectations: a verbal acknowledgement of the potential benefits and risks, and postoperative variation in performance. For instance, cochlear implantation will not restore normal hearing
 - g. Willing to obtain recommended meningitis vaccinations per CDC recommendations
 - h. No reported cognitive issues
 - i. Pass the Mini Mental State Examination (MMSE) screener
 - i. Able and willing to comply with study requirements, including travel to investigational site and study-related activities
- 2. Exclusion Criteria
 - a. Non-native English speaker
 - i. Speech perception materials are presented in English
 - b. Conductive hearing loss in either ear

- c. Compromised auditory nerve, including those with a history of vestibular schwannoma
- d. Ossification
- e. Inability to participate in follow-up procedures (i.e., unwillingness, geographic location)
- f. History of meningitis, autoimmune disease, or any medical condition that contraindicate middle or inner ear surgery or anesthesia
- g. Meniere's disease with intractable vertigo
- h. Trauma that precludes inner ear surgery
- i. Case of sudden sensorineural hearing loss that has not been first evaluated by a physician
- j. Pregnancy
 - i. Subjects who are pregnant or become pregnant prior to surgery are excluded due to the potential risk of anesthesia to an unborn child.
 - a. Subjects who become pregnant after surgery may continue to participate in study procedures
- k. Tinnitus as the primary purpose for seeking cochlear implantation
- 1. Subject obtains a severe or catastrophic score on the Tinnitus Handicap Inventory (Newman, Jacobson & Spitzer, 1996).
- 3. Enrollment
 - a. This study seeks to enroll twenty (20) subjects
- B. Participants: Control group

Subjects must meet the following inclusion criteria and not exhibit any of the exclusion criteria.

- 1. Inclusion Criteria
 - a. Unilateral moderate-to-profound sensorineural hearing loss
 - i. Unaided residual hearing thresholds from 250-8000 Hz (PTA ≥70 dB HL on the implanted side)
 - ii. Normal to mild residual hearing thresholds from 250-8000 Hz in the contralateral ear ≤35 dB HL at each frequency, 250-8000 Hz
 - b. Recipient of bone-conduction device on affected side
 - i. Recipient of the Bone-Anchored Hearing Aid (BAHA)
 - a. Either the Cochlear BAHA Connect or Attract system
 - ii. At least 12 months of listening experience with the BAHA system
 - c. Greater than or equal to 18 years of age
 - d. Duration of moderate-to-profound sensorineural hearing loss less than or equal to 5 years at time of implantation with bone-conduction device (BAHA)
 - i. Either reported by the subject or documented in previous audiograms
 - e. Willingness to participate in test battery
- 2. Exclusion Criteria
 - a. Non-native English speaker

- i. Speech perception materials are presented in English
- b. Conductive hearing loss in either ear
- c. Compromised auditory nerve, including those with a history of vestibular schwannoma
- d. Inability to participate in test battery
- 3. Enrollment
 - a. This study seeks to enroll at least 10 subjects in the control group
- C. Timeline

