Appendix A graphically depicts the timeline and associated measures

The Candidacy Evaluation and Preoperative Evaluation can either occur during the same visit or two different visits.

- 1. **Candidacy Evaluation.** This interval may overlap with the Preoperative Evaluation interval.
 - a. Audiologic Evaluation
 - i. Unaided air- and bone-conduction thresholds in both ears
 - a. Air-conduction assessed with inserts
 - ii. Unaided word recognition in both ears
 - a. Measured with recorded CNC words (50-word list)
 - b. Masking provided when appropriate
 - iii. Tympanometry in both ears
 - iv. Aided word recognition in the affected ear
 - a. Measured with recorded CNC words (50-word list)
 - b. Masking applied to the contralateral ear
 - v. Completion of the Tinnitus Handicap Inventory
 - vi. Determine if potential subject meets candidacy criteria
 - b. Medical Evaluation
 - i. Determine if potential subject is healthy enough to undergo cochlear implantation
 - ii. Associated imaging studies
 - a. This is standard of care for these patient populations
 - b. May also be completed at Preoperative Evaluation
 - iii. Discussion of alternative treatment options
 - iv. Determine if potential subject meets candidacy criteria
 - c. Informed Consent
 - i. Review and discussion of consent form
 - ii. Provide time for subject to review consent form and ask questions
 - iii. Provide subject with a signed copy of the completed consent form

2. **Preoperative Evaluation**. This interval may overlap with the Candidacy Evaluation interval.

The Preoperative Evaluation will be completed within 6 months of the surgery date.

- a. Audiologic Evaluation
 - i. Obtain a case history, including but not limited to:
 - a. Onset of hearing loss
 - b. Progression to moderate-to-profound sensorineural hearing loss
 - c. Suspected etiology of hearing loss
 - ii. Unaided air- and bone-conduction thresholds in both ears
 - a. Air-conduction assessed with insert phones
- iii. Unaided word recognition with CNC words in both ears
 - a. Measured with recorded CNC words (50-word list)
 - b. Masking provided when appropriate
- iv. Tympanometry in both ears
- v. Subjects will complete the test battery detailed in section VII.D.
 - a. Two listening conditions:
 - i. unaided
 - ii. bone-conduction test device or BAHA
 - a. The bone-conduction test device will be the Cochlear BAHA Intenso on a headband

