 - b. Mapping will be completed by board-certified audiologists. Mapping procedures will be similar to conventional cochlear implant recipients.
- iv. Counseling on the external device and use

c. One-Month Post-Initial Activation

- i. Completion of test battery listed in VII.D.
- ii. Speech perception assessed with the cochlear implant on and contralateral ear masked
 - a. CNC words
- iii. Mapping of the external speech processor
- d. Three-Months Post-Initial Activation
 - i. Completion of test battery listed in VII.D.
 - ii. Speech perception assessed with the cochlear implant on and contralateral ear masked
 - a. CNC words

- iii. Mapping of the external speech processor
- e. Six-Months Post-Initial Activation
 - i. Completion of test battery listed in VII.D.
 - ii. Speech perception assessed with the cochlear implant on and contralateral ear masked
 - a. CNC words
- iii. Mapping of the external speech processor
- f. Nine-Months Post-Initial Activation
 - i. Completion of test battery listed in VII.D.
 - ii. Speech perception with the cochlear implant on and contralateral ear masked a. CNC words
- iii. Mapping of the external speech processor
- g. Twelve-Months Post-Initial Activation (study endpoint)
 - i. Completion of test battery listed in VII.D.
 - a. Additional listening condition: bone-conduction test device or BAHA
 - ii. Speech perception with the cochlear implant on and the contralateral ear masked
 - a. CNC words
- iii. Mapping of the external speech processor
- D. Test Battery

The following test battery will be completed at each assessment interval (preoperative, and 1, 3, 6, 9 and 12 months postoperatively). All assessment and mapping will be conducted at the Carolina Crossing research lab by a board-certified audiologist.

- 1. Unaided Diagnostic Assessment
 - a. Air-conduction thresholds in both ears
 - i. Air-conduction assessed with insert phones
 - ii. Assess bone-conduction thresholds if there is a PTA shift of >15 dB as compared to the previous interval
- 2. Tympanometry for each ear
- 3. Sound Field Measures

The Carolina Crossing research lab features a 180° arc with 11 speakers spaced 18° apart. This arc will be utilized during the speech perception and localization measures.

Postoperative aided sound field assessment will be completed with the subject listening with the Opus 2 speech processor.

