 - 1. Subjects will participate in two aural rehabilitation sessions with a board-certified speech-language pathologist. One session will be after the initial activation of the external speech processor. This will occur either on the same day as the initial activation or within the first 2 weeks of listening experience. The second session will be scheduled in conjunction with the 1-month post-initial activation interval.

VIII. Proposed Claims

- A. Demonstrate the effectiveness of cochlear implantation in SSD subjects
 - 1. Demonstrate an improvement in speech perception abilities, localization, and/or subjective benefit in an aided (cochlear implant on) versus an unaided (cochlear implant off) condition
- B. Cochlear implantation provides similar or superior speech perception, localization, and/or quality of life as compared to that found with bone-conduction devices
 - 1. Comparison with control group performance
 - 2. Comparison within subject when listening with bone-conduction test device

IX. Statistical Analysis

- A. Descriptive summaries will be provided for the following: subject demographics, and frequency of major and minor complications/adverse events.
- B. A single-subject design will be utilized, where each subject serves as his or her own control, for analysis of objective and subjective results. A single-subject design was chosen in order to accommodate the heterogeneity that is well known to characterize auditory prosthesis research. Repeated-measures ANOVA will be calculated with a p-value of ≤ 0.05 for statistical significance. Statistical analysis will be conducted with SPSS software.
 - 1. Comparison of aided speech perception performance on word and sentence materials in the post-initial activation intervals to evaluate trends over time

- a. Comparison of the difference between the aided and unaided conditions at each follow-up interval
- 2. Comparison of localization abilities in the post-initial activation intervals
 - a. Comparison of the difference between the aided and unaided conditions for each follow-up interval
 - b. Compute the overall rms error, random error, constant error, and adjusted constant error, as described by Grantham et al (2007)
- 3. Comparison of subjective report scores in the post-initial activation intervals

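### In the between-group comparison (Claim B.1), practice with the speech tests cannot be separated from device: controls take the battery once, implant subjects are on their second to sixth visit

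*Combined protocol and SAP*

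**What the plan says.** **Controls.** Section VI.B.2 schedules "One evaluation interval to complete the test battery outlined in section VII.D", and VI.C.2 makes that visit the control endpoint: "Completion of the test battery (1 interval) defined in section VII.D". Eligibility (VII.B.1.b) requires "At least 12 months of listening experience with the BAHA system".

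**Implant subjects.** Section VII.D states: "The following test battery will be completed at each assessment interval (preoperative, and 1, 3, 6, 9 and 12 months postoperatively". Appendix A shows the same schedule. The study endpoint in VI.C.1 is "The 12-months post-initial activation interval". Before surgery the battery is run under "Two listening conditions" (VII.C.2: unaided, and bone-conduction device). At follow-up it is run with the processor off and on (VII.D.3). The 12-month visit adds one more: "Additional listening condition: bone-conduction test device or BAHA" (VII.C.4.g).

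**The comparison.** Claim B in section VIII is that the implant gives results as good as or better than bone-conduction devices. Item B.1 rests this on "Comparison with control group performance".

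**Not stated.** The plan has no familiarisation run, no rule for assigning word or sentence lists, and no second control visit. It does not say which implant visit is used for B.1, or which listening conditions controls are tested in. Section IX plans repeated-measures ANOVA within implant subjects and names no model for implant against control.

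**The concern.** Listeners may score better on a speech-in-noise test once they know the task, the talkers and perhaps the material. If so, the implant group brings that gain to Claim B.1 and the control group does not. A difference in favour of the implant could then appear with no device difference, and a true bone-conduction advantage could shrink until the devices look similar. More controls would not help, because exposure differs completely between the groups.

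The background section criticises an earlier comparison because its subjects had little experience with the alternative devices, and it proposes long-term users as the remedy. The 12-month BAHA criterion carries this out for experience with the device. It does nothing for experience with the tests.

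**Working it through.** **1. Visits.** Implant: 1 preoperative + 5 post-activation (1, 3, 6, 9, 12 months) = 6. Control: 1. Whichever post-activation visit is chosen for B.1, the implant subject is on visit 2, 3, 4, 5 or 6. No control score comes from a second visit, and no post-activation implant score comes from a first.

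**2. Condition-runs before the 12-month visit.** Preoperative: 2 (unaided, bone-conduction). Months 1, 3, 6 and 9: 4 visits × 2 (processor off, on) = 8. Total 2 + 8 = 10, against 0 for controls within the study.

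**3. The plan's own figures.** Section VII.A.3 sets 20 implant subjects and section IX allows about 20% dropout: 20 × 0.8 = 16 completers. Section VII.B.3 sets at least 10 controls. The plan gives no effect size, SD or power, so there is no power figure to reproduce.

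**4. Sensitivity to an assumed practice gain.** The documents give no gain, no between-subject SD and no test for B.1. Assumptions: true device effect zero; gain *g* of 2, 5 or 8 points in implant subjects only; SD *s* of 10 or 15 points; two-sample t-test, two-sided 0.05.

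- Noncentrality: δ = (*g*/*s*) / √(1/n₁ + 1/10), with n₁ + 8 degrees of freedom.
- False implant superiority = P(T > t₀.₉₇₅), with T noncentral t. With *g* = 0 it is 2.5%.
- n₁ = 16: √(1/16 + 1/10) = 0.403, critical t = 2.064. n₁ = 20: √(1/20 + 1/10) = 0.387, critical t = 2.048.
- Example: *g* = 5, *s* = 10, n₁ = 16 gives δ = 0.5/0.403 = 1.24 and a rate of 22.1%.

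| Assumed gain | SD 10, n₁ = 16 | SD 10, n₁ = 20 | SD 15, n₁ = 16 | SD 15, n₁ = 20 |
|---|---|---|---|---|
| 2 points | 6.9% | 7.2% | 5.0% | 5.2% |
| 5 points | 22.1% | 23.8% | 12.2% | 13.0% |
| 8 points | 47.8% | 51.4% | 24.5% | 26.4% |

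**5. Effect of a same-visit difference.** Let an implant subject's scores be U + *p* unaided and U + D + *p* aided, with *p* the practice gain. Aided minus unaided is D, so *p* cancels if it is the same in both conditions. Compared on aided level alone, the bias is the whole of *p*. The price is variance: with equal SDs and correlation ρ between conditions, the SD of the difference is *s*√(2(1 − ρ)), which exceeds *s* when ρ is below 0.5.

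**The case against.** **The size is assumed.** No section reports a practice effect, and the rates in the table describe a test that the plan does not name. At a 2-point gain the excess is small. This stands: the table shows sensitivity and does not estimate the bias.

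**Localization may be little affected.** Section VII.D.3.c gives no feedback, picks the source at random and varies the level. The background cites a bilateral-implant study in which localization did not differ significantly between two tests 10 months apart. This stands, and the point is strongest for the speech tests.

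**Other comparisons are balanced.** On against off, and Claim B.2 at 12 months, compare conditions in the same subject at the same visit. The questionnaires used for B.1 are not clearly open to test practice. B.1 is a secondary aim of a feasibility study. All of this stands and limits the scope.

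**Stronger readings that the documents do not support.**
- A reader might infer that the net bias in B.1 favours the implant. Practice is only one difference between non-randomised groups. Controls may have used their device for well over 12 months, and implant subjects are selected for dissatisfaction with, or discontinued use of, an earlier option (VII.A.1.d).
- A reader might infer that implant subjects hear repeated lists, or count 40 to 100 AzBio lists before month 12 (10 runs × 4 to 10 scores). The plan is silent on list assignment, and that count assumes one list per score.
- A reader might take controls to be wholly unpractised. That is known only of study visits; the documents do not mention earlier clinical testing.

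None of these limits removes the imbalance in step 1. No part of the plan corrects for it in B.1.

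**Conclusion.** The point holds for the speech tests in Claim B.1, and possibly to a small extent for localization. Test exposure is fully confounded with group: one visit against a second to sixth, with 10 condition-runs before the 12-month visit against none. This follows from the schedule and needs no assumption.

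The direction is conditional: if practice helps, this component favours the implant. The size is unknown. Under the assumptions in step 4, false implant superiority would occur in about 5-7%, 12-24% or 25-51% of trials for gains of 2, 5 or 8 points, against 2.5%.

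It would be wrong to read this as undermining the primary endpoint or Claim B.2 at 12 months. It limits how far a speech-test advantage in B.1 can be attributed to the device, and it can be reduced cheaply.

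**What to change.** 1. **Familiarisation (VI.B.2 and VII.D).** Before scored testing, give each control a short unscored run: one list for each speech-in-noise test and one localization block.
2. **Lists (VII.D).** At the 12-month implant visit and the control visit, use word and sentence lists not previously heard in the study, where the pool allows.
3. **Analysis (IX).** For the speech and localization parts of B.1, also compare aided-minus-unaided scores from the same visit in both groups. State the device-off and device-on conditions for controls, which VII.D now words only for the implant processor. State which implant visit is used.
4. **Drift, descriptive only.** Report the implant group's change from preoperative unaided to 12-month processor-off. Note that loss of residual hearing, a listed risk in XI.A, may affect it. It should not be a threshold for claiming superiority, since that would set two noisy estimates against each other without error control.

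**Cost.** A few more minutes at the control visit, where fatigue is already a listed risk; a list-assignment sheet; and one added analysis on a difference score that may be noisier. Practice runs reduce the imbalance but do not fully remove it, and the difference score removes only a gain that is equal in both conditions.
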